4 TRIAL SETTING

English local authority departments of Children's Social Care:

- Bristol City Council
- South Gloucestershire Council
- Nottinghamshire County Council

Between them, these three councils represent both urban and rural settings, and small and large departments. Bristol and Nottinghamshire have particularly diverse populations.

5 ELIGIBILITY CRITERIA

5.1 Subject population

The intervention is directed at Personal Advisors, but the intended beneficiaries are young people leaving care. The legal definition of a care leaver is someone who has been in the care of the Local Authority for a period of 13 weeks or more spanning their 16th birthday [The Children (Leaving Care) Act 2000].

5.2 Inclusion criteria – Care Leavers

Care leavers aged over 16 years at baseline, allocated to the Leaving Care team for the first time, in a fourmonth period beginning 2 months prior to baseline data collection

5.3 Exclusion criteria – Care Leavers

Care leavers will be excluded if they are:

- living in foster care (other than 'Staying Put' foster care) or in a residential or secure setting of any kind, including custody, remand or hospital; or
- they are simultaneously on the caseload of a qualified social worker for reasons other than being a care leaver, for example, as a result of being a parent themselves; or
- deemed by the local authority to present a risk to themselves or to research staff.

6 TRIAL PROCEDURES

The study aims to recruit all Personal Advisors employed by the participating local authorities, and 60 Care Leavers, 30 from each arm of the trial. This section outlines the key trial procedures from identification of potential participants through to end of trial.

6.1 Schedule of trial assessments and outcomes (overview)

Tables 1 and 2 (next page) depicts the key assessments/outcome measures and participant-related procedures scheduled at various trial timepoints. To summarise, participants in the trial will undergo:

- Identification and screening contact; detailed in Sections 6.2 6.6.
- Consent and randomisation (enrolment); detailed in Section 6.7.
- Assessments at baseline (0-weeks) and follow up at 24- and 48-weeks post-intervention; detailed in Section 6.8.2.

Study data will be collected from i) Personal Advisors, ii) their managers, and iii) care leavers.

6.2 Identification and screening of potential participants (overview)

Participating Local Authorities will be provided with a clear explanation of the purpose and design of the study, and ensure, as far as possible, that the concerns of individual PAs, line managers and other key stakeholders in the LA are addressed.

Personal Advisors will receive notification of the study from the local authority and be invited to attend a briefing session (face to face or online, depending on circumstances.

Eligible care leavers will be identified by the local authority and invited to participate in the study.

6.3 STEP 1: Participant identification and invitation to participate

Personal Advisors will be accessed via their line managers, who will distribute a Participant Information Leaflet designed for local authority staff. Whilst Personal Advisors may be expected by their employer to participate in the trial, we will nonetheless require their informed consent to do so.

All information provided, both written and verbal, will emphasise that the study is testing the effectiveness of a training intervention rather than the practice of individual PAs or teams.

No Personal Advisor will be pressured to participate, and their voluntary participation will be made clear in our recruitment/consent process.

Care Leavers will be notified of the study through their Local Authority, who will forward an invitation to participate from the research team, together with a Participant Information Leaflet (PIL) designed for Care Leavers. The invitation and PIL will make it clear that the decision to take part or not to take part, is entirely voluntary and will have no effect on the services they receive. Details of the research team will be included on the invitation so potential participants can contact the team directly, should they wish to do so.

In addition, a member of the Research Team will attend drop-in sessions (or similar) organised by the Leaving Care team (with their permission) to talk to care leavers about the study. Drop-in sessions usually take place on Local Authority premises, and we will ensure that we can speak to Care Leavers in confidence if they wish. We will reassure young people that they are not obliged to take part.

6.2 STEP 2: Preliminary (eligibility) screening (Care Leavers) and expression of interest

Following an expression of interest from a care leaver, a member of the Research Team will arrange to meet with them to ascertain eligibility, ensure that they fully understand what they study will entail, that they are willing to proceed, and understand that they can withdraw at any time without giving any reason, and without

prejudice to the services they receive. This meeting may be online or in person, depending on circumstances.

The recruitment of Care Leavers will extend beyond the randomisation of PA groups until the training of PAs in the experimental group has been completed.

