3.1 Project timetable

3.3 Planned recruitment rate

Personal Advisors

Participant personal advisors will be recruited from each of the participating local authorities. Whilst the local authority can require their staff to participate, and our aim is to recruit all PAs employed in the local authority, we intend to give personal advisors the option to withhold their consent to participate. In this feasibility study we are aiming to recruit from three groups of PAs at each of three local authorities.

Care Leavers

Participating care leavers will be recruited from each local authority until the target sample is reached (60 care leavers).

Recruitment will be proportionate to the size of the local authority and the flow of eligible care leavers and drawn equally from both arms of the study. We have not conducted a formal sample size calculation but are aiming to demonstrate the feasibility of a definitive RCT by recruiting around 20 care leavers at each of the three local authorities.

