6.3 STEP 3: Informed consent

Following discussion with a member of the research team, both personal advisors and care leavers who wish to participate will be asked to sign a form indicating their informed consent.

6.4 STEP 4: Baseline (first study) appointment (for those potentially eligible in Step 3)

Baseline data will be collected once informed consent has been obtained from PAs and CLs.

As with recruitment, the collection of baseline data from Care Leavers will continue beyond the allocation of PA groups to the trial up to the completion of the training by PAs in the experimental group, but will not continue beyond that point.

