6.5 STEP 5: Randomisation

Once baseline data have been obtained from all relevant Personal Advisors randomisation will be undertaken by [name] at the Bristol Trials Centre and communicated to the local authority groups by a member of the Study Team.

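### Some care leavers can be identified, invited and baselined after their Personal Advisors' group is allocated, with no stated safeguard against arm-dependent selection or early exposure

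*Protocol*

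**What the plan says.** **Order of events.** Randomisation waits only for the PAs' own baseline (section 6.5: "Once baseline data have been obtained from all relevant Personal Advisors randomisation will be undertaken by" a person at the Bristol Trials Centre). On care leavers, section 6.2 (Step 2) says: "The recruitment of Care Leavers will extend beyond the randomisation of PA groups until the training of PAs in the experimental group has been completed". Section 6.4 (Step 4) adds that "the collection of baseline data from Care Leavers will continue beyond the allocation of PA groups to the trial", with completion of training as the last permitted point.

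**Who learns the allocation.** Section 6.5 has it "communicated to the local authority groups by a member of the Study Team".

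**Who controls entry.** Section 6.2 (overview): "Eligible care leavers will be identified by the local authority and invited to participate in the study". Under section 6.3 (Step 1) the local authority also forwards the invitation. Section 5.3 excludes anyone "deemed by the local authority to present a risk to themselves or to research staff". Research staff from Bristol then screen and take consent (sections 6.2 Step 2, 6.3 Step 3 and 14.1).

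**Balance.** Section 3.3 wants care leavers "drawn equally from both arms of the study", and section 6 sets 30 per arm.

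**Blinding.** Section 3 covers those who collect follow-up data. Section 6.11 covers peer researchers' interviews.

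**Timetable (section 3).** Care leaver recruitment and baseline, months 2–6; randomisation, months 5–6; training, months 5–7.

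**The concern.** In a cluster trial, individuals who enter after their cluster is allocated can be identified, approached, excluded or persuaded differently by arm. Here the body that learns the allocation is also the one that finds care leavers, passes on the invitation and judges who is too much of a risk to include.

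The second issue is the baseline. If a care leaver's PA is in the intervention arm and has begun training, an assessment labelled baseline may already reflect that training.

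What is at stake is what the trial was set up to learn: whether care leavers can be recruited and retained in each arm (section 2.2), how scores are distributed and whether they show floor or ceiling effects at baseline (Trial Summary, section 2.3), and whether this recruitment procedure should be reused in a definitive trial. The order of recruitment cannot be undone in the analysis.

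**Working it through.** **1. No powered figure to reproduce.** Section 10.1 states that no sample size calculation was made. The target is self-consistent: 3 authorities × 20 (section 3.3) = 60 = 2 arms × 30 (section 6).

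**2. Share of care leavers entering after allocation.**
Assumptions: even accrual; month m runs from time m − 1 to time m; randomisation falls anywhere from the start of month 5 (time 4) to the end of month 6 (time 6); training ends at the end of month 7.

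Share = (end of recruitment − time of randomisation) ÷ (end of recruitment − start of recruitment). Recruitment starts at time 1.

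| Source of recruitment end | Randomised at time 4 | Randomised at time 6 |
|---|---|---|
| Section 3 timetable (month 6) | (6 − 4)/5 = 40%, 24 of 60 | (6 − 6)/5 = 0%, 0 of 60 |
| Text of 6.2 Step 2 and 6.4 (end of training, month 7) | (7 − 4)/6 = 50%, 30 of 60 | (7 − 6)/6 = 17%, 10 of 60 |

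The timetable closes recruitment in month 6 and training in month 7, whereas the text ties the first to the second. That one-month difference is why there are two ranges.

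**3. Who could have an exposed baseline.** Only intervention-arm care leavers. If late entrants split equally by arm, that is at most 24/2 = 12 of 30 (timetable) or 30/2 = 15 of 30 (text), and fewer in practice, because only those assessed after their own PA's training starts count. Exposure within that group is plausible: section 8.3, Table 1 gives PAs three weeks of applying their action plan in ordinary work before the final session, all of it inside the permitted baseline window. Section 2.7 lists a care leaver measure of the PA's empathy on health, which could respond directly.

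**4. Illustrative size (assumed shift, not from the protocol).** If late intervention-arm entrants differ at baseline by 0.2 to 0.5 SD, through selection or early exposure, the arm mean moves by share × shift. On the text's range this runs from 0.17 × 0.2 = 0.03 SD to 0.50 × 0.5 = 0.25 SD. On the timetable it runs from 0 to 0.40 × 0.5 = 0.20 SD.

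**5. Search for a safeguard.** The blinding statements (sections 3 and 6.11) concern follow-up data collection and peer researchers' interviews. Section 11.3 restricts database access for blinded staff but does not say that recruiters or baseline assessors are among them. Section 13.1 reports eligibility and consent percentages and compares consenters with non-consenters, but not by arm or by timing relative to allocation. No list is fixed before allocation is released.

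**The case against.** The best defence has several parts.

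- **This is a feasibility study.** The analysis is summary statistics and a flowchart (section 10.2), and section 7.1 calls the findings exploratory. Recruitment is a count and retention a proportion of those recruited (section 2.3); neither is defined as a contrast between arms. This stands: a reader might infer a biased treatment effect, but the protocol draws no effectiveness conclusion. It does not protect the arm-specific recruitment figures, the baseline summaries or the procedure carried forward.
- **Only the tail of recruitment is affected.** This stands. Recruitment opens in month 2, the timetable's range includes zero, and accrual stops once 60 is reached (section 3.3). It would be wrong to read the point as covering all care leavers.
- **Baseline contamination is not certain.** This stands. It would also be wrong to say that every care leaver baselined in months 5–7 has a PA in training: control PAs are not trained, and some groups may not yet be allocated. The empathy measure itself is described differently in the Trial Summary (physician empathy) and in section 2.7 (the PA's empathy).
- **University staff do the consenting, and drop-in sessions give a second route.** This is partial cover. The protocol does not say that these staff are unaware of allocation, and the local authority still identifies, invites and excludes. That the particular staff who identify care leavers learn the allocation is an inference, since it is communicated to groups that may be teams or parts of teams. The protocol does nothing to prevent it.
- **Equal numbers per arm do not require recruiters to know the arm.** Correct. Someone must track it, but that can be another person.
- **The eligibility window may close first.** If the four months in section 5.2 run from two months before baseline collection opens in month 2 (time 1), entry to the pool ends at 1 − 2 + 4 = time 3, before the earliest randomisation. That limits who becomes eligible, but invitation, consent and the risk judgement could still follow allocation.

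**Conclusion.** The concern holds in limited form. The protocol states that care leaver recruitment and baseline may run past allocation to the end of training, leaves identification, invitation and a discretionary exclusion with the local authority whose groups are told the result, and keeps no one in that chain unaware of it. Under even accrual, 0–40% of care leavers are affected on the timetable, or 17–50% on the text. Early exposure of the baseline is a risk confined to intervention-arm care leavers assessed after their PA's training starts. The SD shifts above rest on assumed values and show scale only.

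The consequence is possible distortion of arm-specific recruitment and consent, of baseline distributions and floor or ceiling summaries, and of the judgement that this recruitment procedure is fit for a definitive trial. This should be fixed because the remedy is cheap; it does not invalidate the study.

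**What to change.** 1. Before allocation is released, have each local authority supply a dated list of eligible care leavers with the risk exclusion already applied.
2. Complete baselines for those on the list before training starts, where possible.
3. Continue to allow later entrants, identified where possible by someone not told the allocation. Flag them, and report numbers, consent and characteristics by arm and by before or after allocation.
4. Summarise assessments taken after training starts separately from true baselines.
5. Have someone other than the recruiters track the per-arm numbers.
6. Reconcile the month-6 close of recruitment in the section 3 timetable with the end-of-training close in sections 6.2 (Step 2) and 6.4.

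The cost is protocol wording, one dated list per authority, and either a short delay in releasing allocation or slightly fewer late entrants. A strict ban on late entrants or late baselines is not advised: it would trade against the recruitment target that the trial is testing.

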6.3 STEP 3: Informed consent

Following discussion with a member of the research team, both personal advisors and care leavers who wish to participate will be asked to sign a form indicating their informed consent.

6.4 STEP 4: Baseline (first study) appointment (for those potentially eligible in Step 3)

Baseline data will be collected once informed consent has been obtained from PAs and CLs.

As with recruitment, the collection of baseline data from Care Leavers will continue beyond the allocation of PA groups to the trial up to the completion of the training by PAs in the experimental group, but will not continue beyond that point.

6.5 STEP 5: Randomisation

Once baseline data have been obtained from all relevant Personal Advisors randomisation will be undertaken by [name] at the Bristol Trials Centre and communicated to the local authority groups by a member of the Study Team.

6.6 Follow-up assessments

Follow-up assessments of Personal Advisors and Care Leavers will be conducted by members of the study team at 24 and 48 weeks following the completion of PA training. Wherever possible, peer researchers will be responsible for follow-up assessments with Care Leavers, supported by Coram Voice.

6.7 Qualitative assessments

Care Leavers: At 24- and 48 weeks following the completion of training by PAs, we will collect qualitative data from our sample of care leavers on the extent to which they feel their health needs (including emotional health and wellbeing) have been recognized and addressed by their PAs in the previous six months. The interviews will explore how often they have seen their PA; whether PAs have brought up topics covered in training modules (including help seeking, smoking, alcohol and substance use, sexual health, nutrition and exercise); what their own health and wellbeing concerns are and whether or not they have felt able to bring these to the attention of their PA; what the response was, and how helpful their PA has been more generally in helping them to address their health issues. We will also enquire how the CL feels about health issues being raised by the PA, and whether or not they subsequently took any steps to address them.

At the 48 weeks interview we will also ask care leavers about their experiences of participating in the trial, and what their advice would be to a research team wanting to conduct a larger study. A particular focus of this conversation will be their views on the use of peer researchers, the incentives offered; what information they would want to know about the findings of the trial, and in what format.

All interviews with Care Leavers will be conducted via a conference facility or via Smartphone facility, unless and until circumstances change and face-to-face meetings are judged safe and appropriate.

Personal Advisors: At the 24- and 48- week follow up points we will re-interview the same PAs to explore:

- Frequency and content of contacts with CL, with particular focus on module topics;
- which modules have been most, and least, useful; how or why;
- what factors beyond the training have helped them to develop and implement a focus on health promotion activities with care leavers, and what factors have impeded this (factors to be explored

include organisational factors such as supervision, workload, follow-up support; personal factors such as lack of confidence, adverse experiences, and care leaver attributed factors such as lack of interest, refusal to discuss).

Throughout the interviews we will ask for *specific* examples, using these to probe further into the processes underpinning the ways that the training has, or has not, been effective in influencing practice. At 48-weeks we will also ask PAs about their experiences of participating in the trial.

File analysis It will not be possible to observe PAs in action, but we will seek permission from LAs (and CLs) to review the health assessments, pathway plans, and PA records of the care leavers we interview, in both arms of the trial. We will use the files as an additional source of evidence of impact, and to triangulate the data from interviews with PAs.

6.8 Thanking participants for their involvement (payments)

Personal Advisors will not receive any payment for participation. Care Leavers will be offered a £20 voucher at each of the three data collection points, plus travel expenses that might be incurred.

6.10 Emergency contact procedure for participants

We do not anticipate any emergencies arising as a result of this study. However, all participants have either a line manager (in the case of Personal Advisors) or an allocated worker (in the case of Care Leavers) and the Participant Information Leaflets will make clear that any concerns about the study should be addressed to these individuals in the first instance.

6.11 Blinding

Peer researchers will not be told the allocation of the care leavers they interview.

6.13 Withdrawal from the trial (or change of permissions)

Participants can change their permissions of fully withdraw for any reason at any time during their involvement in the trial. Participants can stop: (a) attending the training (in the case of Personal Advisors); and (b) providing questionnaire data to the trial (both Personal Advisors and Care Leavers), at any time for any reason without affecting their employment (Personal Advisors) or service entitlement (Care Leavers).

In all cases, efforts will made to report the reason(s) for the change of permissions in a LIFT Change of permissions/Withdrawal form. The study would also retain, confidentially, any data collected up to the point of withdrawal for analysis, as advised in the PIL.

6.14 End of trial

Participant: The participant ends their involvement with the trial when their last assessment is completed (or they have withdrawn from the study).

6.15 Early termination of the study

The trial may be prematurely discontinued by the Sponsor, Chief Investigator (CI), ethics committee or Funder based on new safety information or for other reasons given by the TSC or ethics committee concerned.

7 INTEGRATED QUALITATIVE RESEARCH

7.1 Integrated qualitative research – experiences and acceptability of study and treatment

Embedded within this feasibility c-RCT is a mixed-method process and implementation study of the training intervention, its use by PAs and the experiences of CLs. This information will aid the interpretation of trial findings (albeit these will only be exploratory) and inform any further adjustments to the intervention or methodology that might be required for a successful Phase III trial.

To address key issues of process and implementation we will observe the training provide in each local authority and to collect the following data from PAs and CLs.

Personal Advisors

After the training we will ask all participants in the experimental arm to complete a questionnaire designed to elicit their perceptions of the value of the training, whether it addressed issues of perceived significance, whether there were any gaps, and how their knowledge has changed, if at all. We will also ask questions about the experience of engaging in a blended learning approach to training, as opposed to face-to-face training in the topics covered.

We will ask Personal Advisors about their perceptions of:

- the relevance of the training to the CLs with whom they work and whether it has given them sufficient knowledge to identify, raise and address the health issues covered (i.e. 'content, 'dose' and 'level');
- the extent to which they think organizational factors are likely to support or impede changes to their practice, including, for example, internal factors such as caseloads; administrative systems, line management support, and external factors such as the availability, capacity and responsiveness of other services;
- what impact they think it might have on their practice, and
- how it might benefit the young people with whom they work.

At the 24- and 48- week follow up points we will re-interview the same PAs to explore:

- Frequency and content of contacts with CL, with particular focus on module topics;
- which parts of the training have been most, and least, useful; how or why;
- what factors beyond the training have helped them to develop and implement a focus on health
 promotion activities with care leavers, and what factors have impeded this (factors to be explored
 include organisational factors such as supervision, workload, follow-up support; personal factors
 such as lack of confidence, adverse experiences, and care leaver attributed factors such as lack of
 interest, refusal to discuss).

Throughout the interviews we will ask for *specific* examples, using these to probe further into the processes underpinning the ways that the training has, or has not, been effective in influencing practice. At 52-weeks we will also ask PAs about their experiences of participating in the trial.

Care leavers

At 24- and 48-weeks, we will collect qualitative data from our sample of care leavers on the extent to which they feel their health needs (including emotional health and wellbeing) have been recognized and addressed by their PAs in the previous six months. The interviews will explore how often they have seen their PA; whether PAs have brought up topics covered in training modules (including help seeking, smoking, alcohol and substance use, sexual health, nutrition and exercise); what their own health and wellbeing concerns are and whether or not they have felt able to bring these to the attention of their PA; what the response was, and how helpful their PA has been more generally in helping them to address their health issues. We will also

enquire how the CL feels about health issues being raised by the PA, and whether or not they subsequently took any steps to address them.

At the 48 weeks interview we will also ask care leavers about their experiences of participating in the trial, and what their advice would be to a research team wanting to conduct a larger study. A particular focus of this conversation will be their views on the use of peer researchers, the incentives offered; what information they would want to know about the findings of the trial, and in what format.

All interviews will be conducted via a conference facility or via Smartphone facility, unless and until circumstances change and face-to-face meetings are judged safe and appropriate.

